### 2.9.2.4 Worsening Hypercapnia

If hypercapnia occurs on transition or during the course of APRV, ensure patency of the endotracheal tube and ventilator circuit, and review the ventilation flow curve and ensure no obstruction.

If these are not concerns you can:

- Increase Phigh in 2 cmH2O increments up to 35 cmH2O while monitoring haemodynamic status
- Reduce Thigh to increase the number of release breaths and therefore increase minute ventilation

### 2.9.2.5 Weaning APRV

Once a patient's clinical condition has improved, clinicians will follow a protocol to wean a patient using APRV that does not involve switching mode to pressure support ventilation, which is the weaning mode most commonly used as standard care.

Once improved (FiO2  $\leq$  40%, SpO2 92-95% and able to sustain spontaneously breathing at a comfortable rate (i.e., 10-30 bpm), APRV should be weaned as follows:

- 1. Progressively increase the inspiratory time ( $T_{high}$ ) by 0.5-1s steps until  $T_{High} > 6$  seconds; and wean the  $P_{HIGH}$  by in 2 cmH2O increments as tolerated to a  $P_{HIGH of}$  15 cmH2O.
  - a. Monitor for desaturation, increased work of breathing, or tachypnea
  - b. When the patient reaches a  $P_{HIGH of}$  10-12 cmH2O, patient can be transitioned to CPAP 10-12 cmH2O without pressure support (PS = 0 cmH2O) and undergo checks for extubation

Participants must continue to receive APRV until extubation to maximise the APRV "dose" received. Remember to optimise sedation to promote more spontaneous breathing.

60	P HIGH = Up or Down –Titrate by 1-2 cmH 2 O to maintain V T >4 and <10ml/kg	Monitor
Weaning	T HIGH + 0.5-1.0 s increments Every 1-2 hours until T high up to 30s Transition to CPAP Optimise Sedation to allow progressively more spontaneous breathing	
 
P0.1
 
ΔPocc
 
RSBI
 
Respiratory Pattern
 

### 2.9.3 Control Arm

Those participants randomised to the control arm will receive current evidence-based best practice adhering to conventional lung protective mechanical ventilation for management of moderate to severe acute respiratory failure.

### Table 5: Evidence-based standard of care

All patients	PaO 2 /FiO 2 ratio<20 kPa
Tidal volume of <6 ml/kg ideal body weight	Prone positioning at least 12 hours per day
Conservative fluid management strategy	Consider ECMO

Faculty of Intensive Care Medicine; Intensive Care Society, and British Thoracic Society endorsed guideline for management of acute respiratory distress (ARDS).[4]

During site initiation visits, sites will be asked to confirm compliance with the evidence-based standard of care outlined above.

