### 2.5.1 Inclusion criteria

- 1. Age ≥ 18 years
- 2. Receiving invasive mechanical ventilation
- Moderate to severe AHRF (PaO2/FiO2 <20kPa with Positive End Expiratory Pressure (PEEP) ≥5 cmH2O) assessed at time of screening (or as documented in the medical record in the preceding 2 hours)
- 4. Expected to stay on invasive mechanical ventilation for >48hrs

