### 2.9.2.2 Challenges potentially encountered during transitioning to APRV

Hypotension

Transitioning from a conventional ventilation mode to APRV may result in transient hypotension. This may be due to unrecognized hypovolemia despite an acceptable blood pressure prior to transition. Ensuring optimal volume status and a starting from a lower Phigh with cautious Phigh up-titration is generally sufficient to blunt the magnitude and duration of hypotension.

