### 2.9.4 Both trial arms

### 2.9.4.1 Refractory Hypoxaemia

If the treating physician is concerned about hypoxaemia, measures such as prone positioning, continuous neuromuscular blockade infusion, inhaled pulmonary vasodilators, or referral for consideration of extracorporeal membrane oxygenation (ECMO) can be applied in either arm of the trial as per standard care in the UK. These interventions will be recorded in the CRF.

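### Table 5 (control arm) and section 2.9.4.1 (both arms) give different rules for proning and ECMO consideration, and nothing says which Table 5 co-treatments apply to APRV patients

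*Protocol*

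**What the plan says.** Section 2.9.3 opens the control-arm description with "Those participants randomised to the control arm will receive current evidence-based best practice adhering to conventional lung protective mechanical ventilation". Table 5 follows under that heading and has two columns. The column for all patients gives a tidal-volume limit and "Conservative fluid management strategy". The column for PaO2/FiO2 below 20 kPa gives "Prone positioning at least 12 hours per day" and consideration of ECMO. Below the table, for site initiation visits, the protocol says that "sites will be asked to confirm compliance with the evidence-based standard of care outlined above".

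Inclusion criterion 3 in section 2.5.1 is "Moderate to severe AHRF (PaO2/FiO2 <20kPa with Positive End Expiratory Pressure (PEEP) ≥5 cmH2O", assessed at screening or from the record of the preceding 2 hours.

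Section 2.9.4.1, under the heading for both trial arms, says that if the treating physician is concerned about hypoxaemia, "measures such as prone positioning, continuous neuromuscular blockade infusion, inhaled pulmonary vasodilators" or referral for consideration of ECMO can be used in either arm in line with UK standard care, and that their use is recorded in the CRF.

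Sections 2.9.1 to 2.9.2.5, which describe APRV, mention neither proning nor a conservative fluid strategy. Section 2.9.4.2 leaves all other management to the attending team.

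**The concern.** Proning has two rules in one protocol. A clinician treating a control patient can read it as listed standard care from the moment of entry, or as an option to use when hypoxaemia causes worry. A clinician treating an APRV patient finds only the second rule.

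The trial is open label (section 2.10.1), so staff know which section describes their patient's arm. If they follow the text literally, controls are proned because Table 5 lists it and APRV patients are proned at discretion. A difference in ventilation duration could then partly reflect co-treatment rather than ventilation mode, which is performance bias.

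ECMO bears on the endpoint directly, because section 2.4.3 counts time on extracorporeal lung support as assisted breathing. Proning could plausibly affect the duration too, in a direction the document does not allow one to predict.

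**Working it through.** The point rests on comparing passages; the only arithmetic is a count.

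**1. Who meets the Table 5 column at entry.** The Table 5 condition is PaO2/FiO2 below 20 kPa. Inclusion criterion 3 is the same ratio below 20 kPa, plus PEEP of at least 5 cmH2O. Anyone who meets the entry criterion therefore meets the Table 5 condition. With 355 planned per arm (section 6.1), that is 355/355 = 100% of controls, and 710/710 of all participants if the table were read as covering both arms. This holds at screening; the ratio may change afterwards.

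**2. The two rules side by side.**

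| | Table 5 (section 2.9.3) | Section 2.9.4.1 |
|---|---|---|
| Placed under | Control arm | Both arms |
| Trigger | Ratio below 20 kPa | Physician's concern about hypoxaemia |
| Proning | Listed as standard, with a daily minimum | Optional, no duration given |
| ECMO | Consider | Referral for consideration, optional |
| Fluids | Conservative, all patients | Not mentioned |

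For proning, the rules differ in trigger and in force. For ECMO, both are softly worded, so the conflict is mainly in the trigger. For fluids, section 2.9.4.1 is silent, so there is no conflict; the gap is only that the APRV arm has no matching statement.

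**3. Whether Table 5 can simply be read as covering both arms.** Its all-patients column limits tidal volume to below 6 ml/kg. Section 2.9.2.3 and the weaning figure in section 2.9.2.5 titrate APRV to above 4 and below 10 ml/kg. Taking the two body-weight bases as equivalent (an assumption), volumes from 6 up to 10 ml/kg lie within the APRV range and outside Table 5. An arm-specific ventilator setting is no fault in itself, but it means the table cannot transfer whole. A site must work out which rows carry over, and no sentence tells it.

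**4. Whether other text closes the gap.**
- Section 2.10.1 describes monitoring of usual care for the control arm, as lung protective ventilation. It describes fidelity monitoring of the intervention, but no check that proning or fluid practice is alike in the two arms.
- Section 3.1 collects use of rescue therapies up to Day 10, and section 2.9.4.1 has proning recorded as a refractory-hypoxaemia measure. As described, a proning record would not show whether it was given as Table 5 standard care or for refractory hypoxaemia.

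**5. Sample size.** The planned total does not depend on this point. It reproduces from a median of 9 against 7 days with exponential times: hazard ratio 9/7 = 1.286; Freedman's formula at two-sided 5% and 90% power gives 673 events; 673/0.95 = 708.4, rounded up to 709, or 710 when made even.

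**The case against.** The best defence is that both passages point to the same standard. Section 2.9.4.1 ties its measures to UK standard care, and Table 5 cites a UK-endorsed guideline. The compliance sentence addresses sites and names no arm. Section 2.9.4.4 trains all sites on standard care for this population. Nothing withholds proning, ECMO referral or conservative fluids from APRV patients, and recording in both arms would make an imbalance visible up to Day 10.

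Much of this stands, and it rules out several stronger readings that a reader might infer:

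- *That co-treatment differs by arm by design.* It does not. The measures are allowed in either arm, and a difference is possible but not prescribed.
- *That fluid strategy is contradicted.* Table 5 puts conservative fluids in the all-patients column, and section 2.9.4.1 does not mention fluids. The phrase "Ensuring optimal volume status and a starting from a lower" in section 2.9.2.2 is a precaution against transient hypotension at transition, not an opposing fluid strategy.
- *That a comparison of rescue therapy would be distorted.* No such comparison is planned: rescue use is not a listed outcome and does not appear in sections 6.2 or 6.3.
- *That the result could not be attributed to ventilation mode.* The trial is pragmatic with a treatment-policy primary analysis, and the document gives no evidence that an imbalance will occur or how large it would be.

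The defence does not remove the conflict over proning and ECMO. A shared reference to UK standard care still leaves a ratio trigger in one place and a concern trigger in the other. The tidal-volume row prevents reading Table 5 as a both-arms table. Recording reveals an imbalance afterwards but does not prevent it.

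**Conclusion.** The point holds as an internal inconsistency that leaves room for performance bias. For control patients, Table 5 and section 2.9.4.1 conflict on the trigger and force of proning and on the trigger for ECMO consideration. For APRV patients, the protocol does not say which non-ventilator rows of Table 5 apply. In an open-label trial this permits, and to a degree invites, an arm difference in proning and ECMO referral. For conservative fluids, the finding is limited to the missing counterpart in the APRV arm.

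The only firm size is that 100% of planned controls (355 of 355) meet the Table 5 threshold at entry. That count shows how widely the conflict applies, not that proning will differ. Any figure in days for the effect on ventilation duration would need assumed shifts with no source in the document, so none is given.

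The conclusion assumes that the CoReCCT master protocol, which is not shown, does not already set one proning and fluid rule for both arms. If it does, a cross-reference would largely settle the matter.

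**What to change.** Reconcile Table 5 with section 2.9.4.1. For each non-ventilator row of Table 5 (proning, fluid strategy, ECMO consideration), state whether it applies to both arms, using one wording and one trigger, and leave only the ventilator settings arm-specific. Which of the existing clinical rules stands is for the sponsor to decide; this review takes no position.

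Then ask sites at initiation to confirm compliance on that basis, have the CRF separate proning given as standard care from proning given for refractory hypoxaemia, and report these co-treatments by arm.

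The cost is small changes to protocol, training and CRF wording, with no extra participants. The summary schedule in section 3.1 names no fluid item, so reporting fluid management by arm may need one data field. Depending on the rule kept, either sites lose some discretion or Table 5 becomes less prescriptive. The change is best made early, because a co-treatment difference cannot be undone once patients have been treated.

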### 2.9.3.1 Weaning in the control arm

Weaning will be conducted according to the usual practices of the participating site (low level pressure support, CPAP or T-Piece) and may or may not include a spontaneous breathing trial. In general criteria for weaning comprise the following:

- o FiO₂ ≤0.40
- PEEP  $\leq 8 \text{ cmH}_2\text{O}$
- Patient has acceptable breathing efforts
- Systolic blood pressure > 90 mmHg without vasopressors

### 2.9.4 Both trial arms

### 2.9.4.1 Refractory Hypoxaemia

If the treating physician is concerned about hypoxaemia, measures such as prone positioning, continuous neuromuscular blockade infusion, inhaled pulmonary vasodilators, or referral for consideration of extracorporeal membrane oxygenation (ECMO) can be applied in either arm of the trial as per standard care in the UK. These interventions will be recorded in the CRF.

### 2.9.4.2 Other Clinical Management

Responsibility for all other management decisions remains the responsibility of the attending physicians and CCU team.

The intervention (APRV or control) will continue until one of the following criteria is met:

- 60 days after randomisation
- Successful unassisted breathing (at 48 hours with no further requirement for inspiratory support or extracorporeal lung support. See section 2.4.3 for full definition)
- Trial intervention-related serious adverse event
- Death or discontinuation of active treatment
- Withdrawal of consent

### 2.9.4.3 Crossover

Crossover from the control arm to APRV will not be allowed. This will be monitored during the trial. If any site despite re-training continues to experience crossover, the site will be closed to recruitment.

We will allow brief periods of conventional ventilation (maximum of 6 hours) for patients randomised to APRV for the purposes of:

- Transport out of the CCU for diagnostic or surgical procedures or other purposes
- Management of a new complication that would be considered an exclusion criterion such as a new air leak or cardiovascular instability

### 2.9.4.4 Site Staff Training

All sites will complete a training package prior to opening to recruitment. The training package will include set up, optimisation, and weaning of APRV; trouble shooting guides; and a review of standard of care approaches for the management of patients with moderate to severe AHRF.

### 2.9.5 Compliance/contamination

Each day, we will record the APRV settings for participants randomised to the intervention arm or ventilator settings for participants randomised to standard care. The statistical analysis plan will define adherence to the trial intervention.

### 2.10 Blinding

### 2.10.1 Methods for blinding and measures to avoid bias

Our trial is an open-label pragmatic design. This design means that patients, clinicians and outcome assessors are aware of treatment allocation. Although we considered blinding during trial design meetings, this is not feasible as we cannot blind clinical teams to ventilator settings. These and the patient response must be visible to guide clinical decision making and ensure patient safety. While lack of blinding can introduce bias, we have safeguards in place to mitigate against this risk as described below.

To mitigate against potential sources of bias with an open label design, we will:

- undertake source verification (from the electronic (or paper) medical record) to minimise the
  risk of reporting bias. The main clinical and resource utilisation outcomes of this trial (e.g.,
  ventilation duration, death, length of stay and adverse events) are recorded
  contemporaneously in the patient medical record by a member of the clinical team as part of
  routine documentation.
- use duration of ventilation as our primary outcome as this is objectively measured and documented in the medical record. Other secondary outcomes are objective; only health-related quality of life requires participant self-report.
- use a short duration of follow-up for the primary outcome (i.e., 48 hours to determine successful extubation) to minimise the risk of attrition bias with withdrawal rates typically < 5% resulting in minimal loss to follow-up. On the rare occasion that a patient or their representative chooses to withdraw, we will retain data collected up until that point and seek permission to continue to collect the main outcome data from their medical records. Our experience is that patients or their representatives normally are happy to proceed on this basis.

- monitor usual care (lung protective ventilation) in the control arm over the duration of the trial to decrease the likelihood of performance bias. We will feedback monitoring data to sites monthly and provide additional training if required.
- collect measures of intervention fidelity over the duration of the trial and feedback monitoring data to sites monthly. If poor fidelity is found, we will provide additional training and support to sites and continue to monitor fidelity. Sites with ongoing issues with intervention fidelity will be closed to recruitment.

We have selected outcomes and measures with demonstrated validity and reliability recommended in the core outcome set for trials of interventions to modify mechanical ventilation duration developed by members of our team ([name] and [name]).[20] Health-related quality of life will be collected by blinded assessors independent of the clinical team involved in delivering the intervention.

We have used the SPIRIT guidelines and checklist to inform the development of our protocol. We will register the trial and will make a full trial protocol publicly available. To ensure our trial reporting is accurate, comprehensive, and transparent, we will use the CONSORT- reporting guidelines to report out trial findings. We will document participant flow through the trial, including screening, baseline and follow up assessments using a CONSORT flow diagram. To avoid selective reporting, we will report all outcomes as outlined a priori in our trial protocol.

We will use Warwick standard operating procedures for trial conduct.

### 2.11 Co-enrolment into other trials

The RELEASE trial investigators will consider co-enrolment of RELEASE trial participants to other interventional trials outside of CoReCCT where there are no possible treatment interaction, and this does not conflict with the trial objectives. Co-enrolment will be permitted with non-interventional observational studies without the need for a co-enrolment agreement. Co-enrolment status will be collected using the eCRF.

# 3. METHODS AND ASSESSMENTS

Data collection will be restricted to variables required to define patient characteristics at enrolment, to monitor interventions received, to monitor adverse effects, to determine quality of life, and to capture the use of hospital healthcare resource. To ensure accurate, complete and reliable data are collected, the research team will provide training to site staff during investigator meetings and site initiation visits. The CTU will provide the PI and research staff with training on the protocol, CRF completion and trial procedures including standard operating procedures (SOPs).

### 3.1 Schedule of delivery of intervention and data collection

The following baseline, clinical, and outcome data will be collected by the local research delivery team from the electronic medical record. In brief the dataset will include:

	Baseline	Day 3	Day 7	Up to Day 10	Up to CCU discharge	Up to hospital discharge	Post-hospital discharge	
					alsonarge		2 months	6 months
Eligibility assessment	x							
Consultee agreement	x							
Baseline data collection	x							
Randomisation	Х							
Ventilator settings, sedation use, organ failure, use of rescue therapies				X				
Serious Adverse Events						x		
Primary outcome					x			
Mortality (secondary outcome)					x	x	х	x
HrQoL (secondary outcome)							х	x
Healthcare utilisation after dx							х	х
Optional blood samples	х	x	x					

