Intervention	Airway Pressure Release Ventilation (APRV). APRV is a method								
	of IMV which uses longer inspiration times followed by a brief								
	expiration. The longer inspiration time enables alveolar								
	recruitment and oxygenation while the short expiration time								
	maintains lung volume. This reduces shear-stress damage to the								
	alveoli, whilst maintaining adequate ventilation.								
Control	Standard lung protective IMV								
Follow-up Duration	6 months								
	Objectives								
Primary Outcome	Duration of invasive mechanical ventilation (time from								
	randomisation to first successful unassisted breathing or death)								
Secondary Outcomes	1. All-cause mortality at 2 and 6 months								
	2. Time to first extubation								
	3. Reintubation								
	4. Use of non-invasive ventilation following extubation								
	5. CCU and hospital length of stay								
	6. Serious adverse events up to hospital discharge								
	7. Health related quality of life (EQ-5D-5L) at 2 and 6								
	months after randomisation								
	8. Acute health care use at 2 and 6 months after								
	randomisation								
	We will conduct a within-trial cost-utility analysis from an NHS								
	hospital care perspective								
Statistical methods	Intention to treat and per protocol analyses.								
	Cox proportional hazard regression model to estimate the treatment								
	difference reporting hazards ratios and their 95% confidence intervals								
	(CIs), using both unadjusted and adjusted estimates.								
	Mean difference with 95% CIs using linear regression.								

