### 6.2.3.2 Primary outcome analysis

Primary outcome and the Estimand Framework

In addition to the objectives, interventions and the population already stated above, the following define the Estimand framework that will be used for the RELEASE trial, in line with the ICH E9 (R1) addendum on Estimand and sensitivity analyses in clinical trials.[23]

Variable (outcome): Our main variable (outcome) of interest is ventilation duration, from the time of randomisation to successful extubation or death. 'Successful extubation' will be defined using the core outcome set[21] definition i.e., the time point a patient is free of ventilatory (invasive or non-invasive) support for >48 hours.

Summary measure and the primary Estimand: Ventilation duration will be determined as the time of successful extubation/death minus the time from the point of randomisation (in hours/mins). The statistical analysis for this outcome will be performed using the treatment policy strategy (i.e., intention-to -treat). Statistical summaries of ventilation duration will be made using median and interquartile range (IQR). We will use a Cox proportional hazard regression model to estimate the treatment difference reporting hazards ratios and their 95% confidence intervals (CIs), using both unadjusted and adjusted estimates. We will report the mean difference with 95% CIs using linear regression.

Intercurrent events (ICEs) and strategies for handling ICEs: post-randomisation events that may affect the interpretation of the primary outcome include: (a) crossover; (ii) non-adherence (including discontinuation of treatment); and (iii) death. Rates of crossover and non-adherence will be added using the principal stratum strategy. We will use the inverse probability weighted analysis method[24] to assess the treatment effect, having taken account of these events. The composite strategy will be used to assess the effect of death, with ventilation duration. We will use the Pocock's win-ratio method[25] and also assess the interaction of ventilation duration with mortality status, bearing in mind the interaction term may not be powered to detect differences.

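### Ventilator data are scheduled only to Day 10 although the allocated mode can run to day 60, and the adherence analysis pairs a principal stratum label with an unspecified weighting method

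*Protocol*

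**What the plan says.** **Data collection.** The schedule in section 3.1 has one row for ventilator data, "Ventilator settings, sedation use, organ failure, use of rescue therapies", marked only in the column ending at Day 10. No other row covers ventilator mode, crossover or adherence. The table is introduced with "In brief the dataset will include". Section 2.9.5 says "Each day, we will record the APRV settings for participants randomised to the intervention arm or ventilator settings for participants randomised to standard care" and gives no last day. It adds: "The statistical analysis plan will define adherence to the trial intervention". Section 2.9.4.3 bars crossover from control to APRV, says it will be monitored during the trial, and closes sites where it persists after re-training. Section 2.10.1 promises fidelity measures over the duration of the trial with monthly feedback. Section 2.9.4.1 has rescue measures entered in the CRF, also without an end day.

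**Treatment period.** Section 2.9.4.2 continues the allocated intervention until unassisted breathing, another listed criterion or 60 days. Section 2.9.2.5 keeps participants on APRV until extubation.

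**Analysis.** Section 6.2.3.2 makes the primary analysis treatment policy. For the other intercurrent events it says "Rates of crossover and non-adherence will be added using the principal stratum strategy", followed by "We will use the inverse probability weighted analysis method". The Trial Summary lists "Intention to treat and per protocol analyses".

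**The concern.** Two things do not fit together.

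First, the one table that tells sites what to collect stops ventilator data at Day 10, while treatment, the crossover ban and fidelity monitoring continue. If sites follow the table, a control patient moved to APRV on day 14, or an APRV patient moved to conventional ventilation on day 12, may leave no trace in the trial data. The observed crossover rate could then be too low, and late deviators could be classed as adherent. A weighted analysis also normally needs time-varying predictors of deviation, and settings, sedation and organ failure all stop at Day 10 in the schedule. A SAP can define adherence, but it cannot recover data that were never collected.

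Second, principal stratum and inverse probability weighting are not natural partners. The usual weighted analysis censors patients when they deviate and reweights the rest. It estimates the effect had nobody deviated, which in the ICH E9(R1) framework that the section invokes is a hypothetical strategy. A principal stratum effect concerns the latent group who would adhere under the assignments that define the stratum. The summary's per-protocol analysis adds a third label that section 6 never takes up.

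**Working it through.** **1. The plan's own figure.** Inputs from section 6.1: control median 9 days, reduction 2 days (so 7), 90% power, 5% significance (taken as two-sided), 5% loss. With exponential times, HR = 7/9.

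- Freedman events: (1.960 + 1.282)² × [(1 + 7/9)/(1 − 7/9)]² = 10.51 × 64, about 673. Divided by 0.95 this is 709, or 710 in equal arms.
- Schoenfeld events: 4 × 10.51/[ln(7/9)]², about 666. Divided by 0.95 this is 702.

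The stated 710 reproduces, so medians of 9 and 7 days are a fair reading of the planning assumptions.

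**2. Patients still ventilated at Day 10.** S(10) = 2^(−10/median).

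| | Control (9 days) | APRV (7 days) |
|---|---|---|
| S(10) | 2^(−10/9) = 0.463 | 2^(−10/7) = 0.371 |
| Patients of 355 | 164 | 132 |
| Share of ventilator time to day 60 after Day 10 | 46% | 37% |

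Together 164 + 132 = 296 of 710. The last row is [S(10) − S(60)]/[1 − S(60)].

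**3. Sensitivity to shape.** The protocol states no distribution. With S(t) = exp[−ln 2 × (t/median)^k] and k from 0.8 to 1.5, between 31% and 47% of patients are still ventilated at Day 10, and 18% to 55% of ventilator time to day 60 falls after it.

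**4. What a missed crossover could do in the pilot.** Table 2 sets green below 4%, amber at 4–5% and red above 5%. With 78 patients, 3/78 = 3.8% is green and 4/78 = 5.1% is red; no whole number of patients falls in amber. One unrecorded late crossover could move this criterion from red to green.

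**5. How far the two estimands can differ (illustration only).** Assume exponential times, a control mean of 9/ln 2 = 12.98 days, and non-adherers who would gain nothing from APRV.

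- Effect among adherers: 12.98 × (7/9 − 1) = −2.89 days.
- Effect if all adhered, with 10% non-adherers: 0.9 × (−2.89) = −2.60 days.
- The same with 20% non-adherers: 0.8 × (−2.89) = −2.31 days.

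If the effect is the same in both groups, the two estimands coincide.

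**The case against.** The strongest reply is that the protocol never says mode is unrecorded after Day 10. The table is a summary, three other sections set no such limit, and data-collection detail is referred to a master protocol that is not to hand. Adherence is left to the SAP, which may use a fixed early window. That would suit a trial of early APRV, and section 4.1 applies the same Day 10 limit to pre-specified complications. This stands in part: the defect is a conflict to reconcile, and a reader who inferred that late crossover is certain to be invisible would go beyond the documents. Two things limit the reply. Section 3 restricts collection to required variables, so capture outside the schedule cannot be presumed. Section 4.1 also shows that Day 10 is a working cut-off in this trial.

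It is also fair that the 296 are patients still ventilated, not deviators. As an illustration at the pilot's 5% red limit, 0.05 × 710 = 35.5 patients cross over; if 46% of these first did so after Day 10, about 16 patients (2.3% of 710) would be missed. The documents give no figure for APRV-arm non-adherence. The primary outcome also counts non-invasive and extracorporeal support, whereas APRV ends at extubation. If the medians reflect that outcome, the time needing a mode record is somewhat overstated.

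On the estimand, section 6.2.3.2 does not define its weights. Principal-score weights can target a principal stratum effect under principal ignorability, so the mismatch is likely but not proven. The choice of weights can be left to the SAP. What the protocol itself fixes is a strategy label next to a method that usually answers a different question, with a reference whose title concerns crossover and statistical power.

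**Conclusion.** The concern holds as an internal inconsistency with practical consequences. Followed as scheduled, data collection would cover only the first 10 of up to 60 treatment days, with 37% to 46% of patients per arm still ventilated at that point (31% to 47% across the shapes tried). These figures rest on medians of 9 and 7 days counted from randomisation and an assumed exponential or Weibull form. Crossover could be understated, including against the pilot's progression limits, and late deviators could be misclassified in the supplementary adherence analysis. That analysis also carries a strategy label that probably does not match its estimator.

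A reader might infer that the adherence results would be wrong. The documents do not support that: the rate of late deviation is unknown, no bias has been quantified, and the SAP may limit adherence to an early window. The primary treatment-policy analysis and N = 710 are not affected.

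**What to change.** - **Data.** Reconcile the schedule in section 3.1 with sections 2.9.4.3, 2.9.5 and 2.10.1. Keep full settings to Day 10. After that, add a brief daily record for patients still receiving the intervention: APRV yes or no, hours off the allocated mode, and the few covariates the weighting model needs. End it when the intervention ends.
- **Estimand.** In section 6.2.3.2, match strategy to estimator. Either name a hypothetical strategy and use inverse-probability-of-censoring weights, or keep principal stratum and use an estimator that targets it: randomisation as instrument, or principal-score weights with the assumption stated.
- **Summary.** Align the per-protocol wording in the Trial Summary with whichever analysis is chosen.

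The cost is one short eCRF item per ventilated day after Day 10, hence modest site data entry, plus wording changes. The sample size and the primary analysis stay as they are.
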